Appendix B - ACTT-2: Baricitinib/Remdesivir vs Remdesivir

11. Received monoclonal antibodies targeting cytokines (e.g., TNF inhibitors, anti-interleukin-1 [IL-1], anti-IL-6 [tocilizumab or sarilumab]), or T-cells (e.g., abatacept) in the 4 weeks prior to screening.
12. Received monoclonal antibodies targeting B-cell (e.g., rituximab, and including any targeting multiple cell lines including B-cells) in the 3 months prior to screening.
13. Received other immunosuppressants in the 4 weeks prior to screening and in the judgement of the investigator, the risk of immunosuppression with baricitinib is larger than the risk of COVID-19.
14. Received ≥ 20 mg/day of prednisone or equivalent for ≥ 14 consecutive days in the 4 weeks prior to screening.
15. Use of probenecid that cannot be discontinued at study enrollment.
16. Have diagnosis of current active tuberculosis (TB) or, if known, latent TB treated for less than 4 weeks with appropriate anti-tuberculosis therapy per local guidelines (by history only, no screening required).
17. Suspected serious, active bacterial, fungal, viral, or other infection (besides COVID-19) that in the opinion of the investigator could constitute a risk when taking investigational product.
18. Have received any live vaccine (that is, live attenuated) within 4 weeks before screening, or intend to receive a live vaccine (or live attenuated) during the study. Note: Use of non-live (inactivated) vaccinations is allowed for all subjects.
19. Have a history of VTE (deep vein thrombosis [DVT] or pulmonary embolism [PE]) within 12 weeks prior to screening or have a history of recurrent (>1) VTE (DVT/PE).
20. Immunocompromised patients, patients with a chronic medical condition, or those taking a medication that cannot be discontinued at enrollment, who, in the judgment of PI, are at increased risk for serious infections or other safety concerns given the study products.

Study Intervention

Subjects will be randomized into two arms (1:1).

	Baricitinib	Placebo
Remdesivir	Arm 1 Baricitinib tablets + remdesivir IV	Arm 2 Placebo tablets + remdesivir IV

All subjects will receive remdesivir as a 200 mg intravenous (IV) loading dose on Day 1, followed by a 100 mg once-daily IV maintenance dose for the duration of the hospitalization up to a 10-day total course. See Section 6.1.4 for details of dosing and dose modification.

For the baricitinib component, subjects will receive either active product or placebo as follows:

- Baricitinib will be administered as a 4 mg* orally (po) (two 2mg tablets) or crushed for NG tube, daily for the duration of the hospitalization up to a 14-day total course.
- A placebo will be given as two tablets* po or crushed for NG tube, daily for the duration of the hospitalization up to a 14-day total course

** Patients with eGFR <60 mL/min will receive a dose of one tablet (2-mg or placebo) once daily.*

Duration of therapy:

- IV remdesivir – 10 days while hospitalized.
- Oral (baricitinib or placebo) component – 14 days while hospitalized.
- Both stop on discharge from hospital.

1.2 Schedule of Assessments

Table 1. Schedule of Assessments (SOA)

Day +/- Window	Screen	Baseline	Study Intervention Period	Follow-up Visits		
	-1 or 1	1	Daily until hospital discharge	15 ⁷ ± 2	22 ⁷ ± 3	29 ⁷ ± 3
ELIGIBILITY						
Informed consent	X					
Demographics & Medical History	X					
Review SARS-CoV-2 results	X					
STUDY INTERVENTION						
Randomization		X				
Administration of investigational agent			
 • Remdesivir daily infusion until day 10 or discharge. • Baricitinib or placebo: daily by mouth until day 14 or discharge 			
STUDY PROCEDURES						
Targeted physical exam		X				
Vital signs including SpO ₂ ¹		X ⁴	Daily until discharge ⁸	X ⁹		X ⁹
Clinical data collection ²		X ⁴	Daily until discharge ⁸	X ⁹	X ⁹	X ⁹
Adverse event evaluation		X ⁴	Daily until discharge ⁸	X ⁹	X ⁹	X ⁹
Concomitant medication review		X ⁴	From Day -7 to Day 15			
SAFETY LABORATORY						
Safety hematology, chemistry and liver tests	X ³	X ^{4,5,6,7}	Day 3, 5, 8, 11 (all ± 1 day) if hospitalized ^{6,7}	X ⁹		X ⁹
Pregnancy test for females of childbearing potential	X ³					
RESEARCH LABORATORY						
Blood for plasma to test for PCR SARS-CoV-2		X ^{4,6}	Day 3, 5, 8, 11 (all ± 1 day) if hospitalized			
Oropharyngeal swab ¹⁰		X ^{4,6}	Day 3, 5, 8, 11 (all ± 1 day) if hospitalized	X ⁹		X ⁹
Blood for serum (secondary research)		X ^{4,6}	Day 3, 5, 8, 11 (all ± 1 day) if hospitalized	X ⁹		X ⁹

Notes:

¹Vital signs include temperature, systolic blood pressure, heart rate, respiratory rate, O₂ saturation and level of consciousness. Vital signs collected as part of standard care may be used.

²Refer to Section 8.1.2 of the protocol for details of clinical data to be collected including ordinal score, NEWS, oxygen requirement, mechanical ventilator requirement, etc.

³Screening laboratory tests include: CBC with differential (including absolute neutrophil count and absolute lymphocyte count), ALT, AST, creatinine (and calculate an estimated glomerular filtration rate (eGFR) the formula used is determined

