We anticipate that this trial will require 732 recoveries. Assuming that 70% of subjects achieve recovery in 28 days, the total sample size is approximately 1032.

Study Population

Inclusion Criteria

1. Admitted to a hospital with symptoms suggestive of COVID-19.
2. Subject (or legally authorized representative) provides informed consent prior to initiation of any study procedures.
3. Subject (or legally authorized representative) understands and agrees to comply with planned study procedures.
4. Male or non-pregnant female adults ≥ 18 years of age at time of enrollment.
5. Has laboratory-confirmed SARS-CoV-2 infection as determined by PCR or other commercial or public health assay in any specimen, as documented by either of the following:
 - PCR positive in sample collected < 72 hours prior to randomization; OR
 - PCR positive in sample collected ≥ 72 hours prior to randomization, documented inability to obtain a repeat sample (e.g. due to lack of testing supplies, limited testing capacity, results taking > 24 hours, etc) AND progressive disease suggestive of ongoing SARS-CoV-2 infection.
6. Illness of any duration, and at least one of the following:
 - Radiographic infiltrates by imaging (chest x-ray, CT scan, etc.), OR
 - SpO₂ $\leq 94\%$ on room air, OR
 - Requiring supplemental oxygen, OR
 - Requiring mechanical ventilation or ECMO.
7. Women of childbearing potential must agree to either abstinence or use at least one primary form of contraception not including hormonal contraception from the time of screening through Day 29.
8. Agrees to not participate in another clinical trial for the treatment of COVID-19 through Day 29.

Exclusion Criteria

1. ALT or AST > 5 times the upper limit of normal.
2. Estimated glomerular filtration rate (eGFR) < 30 ml/min or patient is receiving hemodialysis or hemofiltration at time of screening.
3. Neutropenia (absolute neutrophil count < 1000 cells/ μ L) ($< 1.0 \times 10^3/\mu$ L or < 1.0 GI/L).
4. Lymphopenia (absolute lymphocyte count < 200 cells/ μ L) ($< 0.20 \times 10^3/\mu$ L or < 0.20 GI/L)
5. Pregnancy or breast feeding.
6. Anticipated discharge from the hospital or transfer to another hospital which is not a study site within 72 hours.
7. Allergy to any study medication.
8. Received three or more doses of remdesivir including the loading dose, outside of the study under the EUA (or similar mechanism) for COVID-19.

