5.2 Exclusion Criteria

1. ALT or AST > 5 times the upper limit of normal.
2. Estimated glomerular filtration rate (eGFR) < 30 ml/min or patient is receiving hemodialysis or hemofiltration at time of screening.
3. Neutropenia (absolute neutrophil count < 1000 cells/ μ L) ($< 1.0 \times 10^3/\mu$ L or < 1.0 GI/L).
4. Lymphopenia (absolute lymphocyte count < 200 cells/ μ L) ($< 0.20 \times 10^3/\mu$ L or < 0.20 GI/L)
5. Pregnancy or breast feeding.
6. Anticipated discharge from the hospital or transfer to another hospital which is not a study site within 72 hours.
7. Allergy to any study medication.
8. Received three or more doses of remdesivir, including the loading dose, outside of the study under the EUA (or similar mechanism) for COVID-19.
9. Received convalescent plasma or intravenous immunoglobulin [IVIg]) for COVID-19, the current illness for which they are being enrolled.
10. Received small molecule tyrosine kinase inhibitors (e.g. baricitinib, imatibib, genfinitib), in the 1 week prior to screening

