6.1.2 Dosing and Administration

All subjects will receive remdesivir as a 200 mg intravenous (IV) loading dose on Day 1, followed by a 100 mg once-daily IV maintenance dose for the duration of the hospitalization up to a 10-day total course.

If subjects already received the loading dose as under the EUA or similar mechanism, then start at 100 mg/day. Any doses of remdesivir under an EUA (or similar mechanism) prior to enrollment will be counted, so the total duration of remdesivir (i.e. EUA + on this trial) is 10 days (i.e., a maximum of 10 total infusions). If one or two doses of remdesivir were administered (under EUA or similar mechanism) prior to study enrollment, this should be documented in eClinical as a concomitant medication given prior to Day 1.

For the baricitinib component, subjects will receive either active product or placebo as follows:

- Baricitinib will be administered as a 4 mg orally (po) (two 2mg tablets) or crushed for NG tube, daily for the duration of the hospitalization up to a 14-day total course.

- A placebo will be given as two tablets po or crushed for NG tube, daily for the duration of the hospitalization up to a 14-day total course.

See Section 6.1.4 for dosing modifications for renal failure.

Dosing of the two medications does not need to occur at the same.

Any dose that is delayed may be given later that calendar day. Any dose that is missed during the study due to any reason (not given that calendar day) is not made up. The treatment course continues as described above even if the subject becomes PCR negative.

Duration of therapy:

- IV remdesivir – 10 days while hospitalized (i.e., maximum of 10 total infusions pre-enrollment and during study).
- Oral (baricitinib or placebo) component – 14 days while hospitalized (i.e., maximum of 14 total doses).
- Both stop on discharge from hospital. If readmitted after discharge, see Section 7.4.

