7.4 Readmission

If a subject is discharged from the hospital and then readmitted prior to Day 14, they may be given the remainder of the study product (i.e., infusion until Day 10 and oral product until Day 14). If the subject did not withdraw his/her consent to participate in the study, there is no need to re-consent upon readmission to the study hospital. However, the site will need to inform them that since he/she was readmitted, study product administration will resume and confirm that they still agree to receive study product. If the subject is re-admitted with diminished mental capacity, the site should discuss continued study participation with a LAR.

The study team will need to notify the study pharmacist of the readmission. The subject will not get the doses that they missed after being discharged. Upon readmission, the subject will get maintenance doses of infusion only since they already received the loading dose of the study product infusion on Day 1. No study product infusions should be given past Day 10 and no oral study product should be given past Day 14.

The site should not complete the Discontinuation of Treatment form in Advantage eClinical since the subject came back to the study hospital to be readmitted. For all data collection procedures required for those readmitted, please see the MOP.

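### The prior-remdesivir dosing rule in Appendix B 6.1.2 is missing from the synopsis, Schedule of Assessments and SAP 4.2.1, which read literally give up to 12 infusions and a second loading dose

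*Protocol*

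**What the plan says.** Entry after limited prior treatment is allowed. Appendix B 5.2, exclusion 8, rules out a patient who has "Received three or more doses of remdesivir, including the loading dose, outside of the study under the EUA (or similar mechanism) for COVID-19", and the synopsis has the same criterion. Zero, one or two prior doses are therefore compatible with enrolment.

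Appendix B 6.1.2 begins with the 200 mg Day 1 loading dose for all subjects and then qualifies it: "If subjects already received the loading dose as under the EUA or similar mechanism, then start at 100 mg/day". It adds that doses given before enrolment count, and it limits the combined total, before and during the trial, to 10 infusions. It states that limit twice.

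The qualification does not appear in three other places that describe the course:

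- Synopsis, Study Intervention: "All subjects will receive remdesivir as a 200 mg intravenous (IV) loading dose on Day 1", followed by "See Section 6.1.4 for details of dosing and dose modification". Its duration line is "IV remdesivir – 10 days while hospitalized".
- Schedule of Assessments, Appendix B 1.2: "Remdesivir daily infusion until day 10 or discharge".
- SAP 4.2.1: the same all-subjects loading-dose sentence as the synopsis.

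Appendix B 6.1.4 deals with laboratory-driven holds and dose changes and has no rule on prior remdesivir. Appendix B 7.4, on readmission, describes the remaining product as "infusion until Day 10 and oral product until Day 14" and presumes that the loading dose was given on study Day 1. SAP 4.2.5, on the timing of doses for each subject, does refer to Appendix B 6.1.2 through 6.1.5.

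**The concern.** For a patient already loaded before enrolment, the passages cannot all be followed as written. Section 6.1.2 stops by a count of infusions that includes those given earlier; the Schedule of Assessments stops by study day. Section 6.1.2 omits the loading dose; the synopsis and SAP 4.2.1 give it to everyone. A site working from the synopsis is sent to a section that does not contain the exception.

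What is at stake is the background exposure of these patients, and whether sites handle them alike. There is also a reporting consequence. SAP Table 4 has a row for patients given all 10 remdesivir infusions, and it accounts for fewer than 10 only by discharge or death. It does not say whether infusions before enrolment count. The Table 4 programming note looks for maintenance doses recorded as not given through Day 10, so a patient who stopped on Day 8 in line with 6.1.2 could be tabulated as having missed doses.

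**Working it through.** Inputs, all from the documents: loading dose 200 mg and maintenance dose 100 mg daily (synopsis, 6.1.2, SAP 4.2.1); prior doses p = 0, 1 or 2 (exclusion 8); combined limit of 10 infusions (6.1.2); last infusion on study Day 10 (Schedule of Assessments).

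Assumptions: the patient remains in hospital through Day 10, misses no dose, and the first pre-enrolment dose was the 200 mg loading dose.

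**Reading A, Section 6.1.2.** On-study infusions = 10 − p. Total = p + (10 − p) = 10, which reproduces the protocol's own limit. There is one loading dose, so total mg = 200 + 9 × 100 = 1100 for every p.

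**Reading B, the Day 10 end with the 6.1.2 loading rule.** On-study infusions = 10. Total = 10 + p. There is one loading dose, so total mg = 200 + 100 × (10 + p − 1).

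**Reading C, the Day 10 end with the Day 1 loading dose for all.** On-study mg = 200 + 9 × 100 = 1100. Prior mg = 200 + 100 × (p − 1) when p is 1 or 2.

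| Prior doses | A: infusions / loading doses / mg | B: infusions / loading doses / mg | C: infusions / loading doses / mg |
|---|---|---|---|
| 0 | 10 / 1 / 1100 | 10 / 1 / 1100 | 10 / 1 / 1100 |
| 1 | 10 / 1 / 1100 | 11 / 1 / 1200 | 11 / 2 / 1300 |
| 2 | 10 / 1 / 1100 | 12 / 1 / 1300 | 12 / 2 / 1400 |

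With two prior doses, reading C exceeds reading A by 1400 / 1100 − 1 = 27%.

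Under reading A the last on-study infusion falls on Day 9 with one prior dose and Day 8 with two. The Schedule of Assessments continues to Day 10 in both cases.

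The two discrepancies have different sources. The Schedule of Assessments line bears only on the number of infusions. The second loading dose comes only from the all-subjects sentence in the synopsis and SAP 4.2.1.

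Section 7.4 needs separate treatment. Its bar on infusions after Day 10 is a ceiling, and a patient who stops on Day 8 under the 10-infusion limit complies with it. It also allows only maintenance doses on readmission. What does not fit is its premise that the loading dose was given on study Day 1, which under 6.1.2 is untrue for a patient loaded beforehand.

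**The case against.** The strongest reply is that nothing is contradictory here: 6.1.2 is the dosing section, it is the only passage that addresses pre-treated patients, and it opens with the same all-subjects sentence before stating the exception. The other passages are general and silent on these patients. A site that reads 6.1.2 has a clear instruction, and SAP 4.2.5 points to it. Much of this stands, and it means the documents should not be described as containing two rival rules for pre-treated patients. It does not remove the gap, because no order of precedence is stated, the synopsis points to a different section, and the Schedule of Assessments has no footnote or exception.

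A second reply is that the synopsis and SAP 4.2.1 limit the course to ten days in total, which could include earlier doses. That is possible, and it would bring the count back to 10. The extra loading dose would remain: with two prior doses, 200 + 100 before enrolment and 200 + 7 × 100 on study makes 1200 mg. It also does not help the Schedule of Assessments, whose end point is a study day.

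Three stronger inferences are tempting and are not supported:

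- That the baricitinib comparison is biased. Both arms receive remdesivir and randomization is stratified by site, so nothing in the documents ties the ambiguity to the assigned arm.
- That the prior-remdesivir subgroup in SAP Table 19 is undermined. It separates any from no prior treatment, and membership does not depend on later infusions.
- That a particular number of patients is affected. The documents do not give the share with prior doses.

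**Conclusion.** The point holds as an inconsistency of wording that bears on patient exposure. The Schedule of Assessments, followed literally, exceeds the protocol's own limit of 10 infusions by one for a patient with one prior dose and by two for a patient with two. The all-subjects sentence in the synopsis and SAP 4.2.1 would add a second loading dose. Twelve infusions and 1400 mg are maxima that require two prior doses, a stay through Day 10, no missed dose, and dosing from those passages without regard to 6.1.2. Patients with no prior remdesivir are unaffected under every reading.

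On the analysis side, the gap is confined to the descriptive compliance table. Table 4 leaves open whether prior infusions count, although the SAP plainly expects such patients: Table 4 has a row for prior remdesivir, and Tables 5 and 6 summarize the number of prior doses. No effect on type I error or power is claimed. This review takes no view on which loading-dose or stopping rule should apply.

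**What to change.** 1. Reconcile the synopsis, the Schedule of Assessments, Appendix B 6.1.2, the loading-dose wording in 7.4, and SAP 4.2.1, so that all state one loading-dose rule and one stopping rule (by infusion count or by study day) for patients with prior remdesivir. The choice belongs to the sponsor.
2. Correct the synopsis cross-reference so that it leads to the section holding the prior-dose rule.
3. State in SAP Table 4, and in its programming note on missed maintenance doses, whether infusions before enrolment count toward the full course of 10. A patient who follows the reconciled rule should not appear as incomplete or as missing doses.

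The cost is wording in an amendment or clarification letter, a sentence in SAP 4.2.1 and a note to Table 4. No new data are needed, because 6.1.2 already has prior doses recorded as concomitant medication.

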Appendix B - ACTT-2: Baricitinib/Remdesivir vs Remdesivir

by the sites, but should be consistent throughout the study), and pregnancy test. Laboratory tests performed in the 48 hours prior to enrollment will be accepted for determination of eligibility.

⁴ Baseline assessments should be performed within 24 hours prior to first study product administration. Results of Day 1 (baseline) laboratory assessment do not need to be reviewed to determine if initial study product should be given.

⁵ Laboratory tests performed as part of routine clinical care in the 24 hours prior to first dose will be accepted for the baseline safety laboratory tests. Baseline may be the same as the screening laboratory tests.

⁶ Safety laboratory tests include WBC with differential, hemoglobin, platelets, creatinine, glucose, total bilirubin, ALT, AST, INR, d-dimer, and C-reactive protein (CRP). Note: D-dimer and CRP values may predict severity and support assessment of outcomes and unlike other safety laboratory values, D-dimer and CRP should not be graded.

⁷ Any laboratory tests performed as part of routine clinical care within the specified visit window can be used for safety laboratory testing. Window during the 10 days of dosing is ± 1 day.

⁸ Daily until hospital discharge or end of study, whichever comes first.

⁹ In-person visits are preferred but recognizing quarantine and other factors may limit the subject's ability to return to the site for the visit. In this case, the visit may be performed by phone. If subject is still hospitalized during the follow-up period, they should get Day 15, 22 and 29 assessments along with the daily clinical data collection.

- If still hospitalized at Day 15 and 29 or returns to the site for an in-person visit: collect clinical data, vital signs, safety laboratory tests, and research laboratory samples (OP swab and serum only) as able.
- If phone call only on Days 15 and 29 and all Day 22 visits: assess adverse events, clinical status (ordinal scale), readmission to a hospital, and mortality only.

¹⁰ Oropharyngeal swabs are preferred, but if these are not obtainable, nasopharyngeal or nasal swabs may be substituted.

1.3 Study Schema

2. INTRODUCTION

2.1 Background

2.1.1 ACTT-2 – Baricitinib/Remdesivir vs. Remdesivir Trial

A preliminary review of data from ACTT-1 occurring after 606 recoveries and 103 deaths (approximately 67% of the 1063 subjects enrolled) demonstrated that subjects that received remdesivir had a 31% faster time to recovery (11 vs 15 days, recovery rate ratio 1.312 (1.119, 1.541), $p < 0.001$), and a decrease in mortality (8.0% vs 11.6%, $p = 0.059$). The DSMB asked that the sponsor be unblinded early given public health implications and implications for ACTT-2. While an antiviral appears to have some efficacy in the treatment of COVID-19, the mortality rate is still high. Infection by pathogenic coronaviruses (e.g. SARS and SARS-CoV-2) often results in excessive cytokine and chemokine action with the development of acute respiratory distress syndrome (ARDS) (33-35). It is postulated that this dysregulated inflammatory immune response is contributing to the excessive mortality, and targeting this response will further improve outcomes.

Baricitinib, an orally administered, selective inhibitor of JAK1 and JAK2, could be a therapeutic option because of the potential to inhibit signaling from multiple cytokines in COVID-19

Appendix B - ACTT-2: Baricitinib/Remdesivir vs Remdesivir

patients (30). Baricitinib inhibits signaling of cytokines implicated in COVID-19, including IL-2, IL-6, IL-10, IFN- γ , and G-CSF, with lower IC50 values translating to a greater overall inhibition of STAT signaling during the dosing interval (33). Baricitinib treatment resulted in a reduction from baseline in serum IL-6 at Week 12 in patients with active RA in a Phase 2, randomized, placebo-controlled study of baricitinib (data on file). The potent anti-inflammatory effects of baricitinib have also been demonstrated by the reduction of serum levels of IFN- γ , IP-10, GM-CSF and MCP-1 in pediatric patients with steroid-dependent chronic inflammation, resulting in control of disease activity and the ability to wean or taper steroids (36).

A recent comment by Richardson *et al.* published in the Lancet (32), suggested a potential role for baricitinib in the treatment of COVID-19. The authors hypothesize that baricitinib, a JAK1/2 inhibitor, will directly mitigate the inflammatory response triggered by SARS-CoV-2 infection. In addition, baricitinib has been identified as a numb-associated kinase (NAK) inhibitor with high-affinity for AP2-associated protein kinase 1 (AAK1-8.2 nM, BIKE-20 nM and GAK-120 nM). AAK1 and GAK were previously described as a crucial regulator of clathrin-mediated endocytosis and propagation of coronavirus and other viruses (37). In light of this, baricitinib may have an unappreciated antiviral effect by attenuating host-cell propagation of the virus in infected COVID-19 patients.

